## 3.9 Device Fit Judged by Clinicians

Device fit analyses will be done for each visit and will be based on the data collected in the Device Position CRF, and includes the following endpoints:

a) Proportion of subjects who can be fitted with Ovaprene®. This is from the CRF questions "Did the Ovaprene® device fit the subject?" (Response: Yes, No). The numerator is the number of clinicians who have answered "Yes", and denominator is the total number of clinicians who have answered the question.

- b) Proportion of subjects who can correctly insert the Ovaprene® device using written instructions only. This is from the question "Was the subject able to insert the Ovaprene® device using:" with response: Only written instructions, Written and verbal instructions, Written and verbal instruction and physical assistance. The numerator is the number of clinicians who have answered "Only written instructions", and denominator is the total number of clinicians who have answered the question.
- c) Proportion of subjects who can correctly position the device using written and verbal instructions. This is from the question "Was the subject able to position the Ovaprene® device using:" with response: Only written instructions, Written and verbal instructions, Written and verbal instruction and physical assistance. The numerator is the number of clinicians who have answered "Written and verbal instructions", and denominator is the total number of clinicians who have answered the question.
- d) Proportion of subjects who can correctly remove the device using written and verbal instruction and physical assistance. This is from the question "Was the subject able to remove the Ovaprene® device using:" with response: Only written instructions, Written and verbal instructions and physical assistance. The numerator is the number of clinicians who have answered "Written and verbal instruction and physical assistance", and denominator is the total number of clinicians who have answered the question.
- e) Location of Ovaprene® in relation to the cervix as determined by digital examination. Categorical summaries will present the number and percent of clinicians who answered with "Over cervical os", "Not over cervical os on anterior vaginal wall", and "Not over cervical os and not on anterior vaginal wall".
- f) Location of Ovaprene® in relation to the cervix, or to the pubic bone, as determined by visual examination. Categorical summaries will present the number and percent of clinicians who answered with "Over cervical os", "Not over cervical os on anterior vaginal wall", and "Not over cervical os and not on anterior vaginal wall". Furthermore, for "Not over cervical os on anterior vaginal wall", more details are asked: "Was the anterior edge of the device behind the pubic bone?" (Yes, No, Unable to tell); "If it was not behind the pubic bone, did you attempt to push it behind the pubic bone?" (No, Yes), "If Yes, were you successful?" (Yes, No). All these answers will be summarized categorically.
- g) Each subject will have the following data summarized to compare clinician assessment of position to dislodgements reported in the subject e-diary:
  - Proportion of clinician assessments of displacement (displaced being defined as Not over cervical os - on anterior vaginal wall or Not over cervical os and not on anterior vaginal wall using either visual or digital examination)
  - Number of complete expulsions on the diary
  - Number of partial displacements on the diary
  - Response at end of study to acceptability question: While you have already had tubal sterilization, if you needed protection against pregnancy, how likely would you be to use Ovaprene® if it became available?

- Response at end of study to acceptability question: How likely would you be to recommend Ovaprene® to a friend who needed protection against pregnancy if Ovaprene® became available?
- Had vaginal deliveries
- h) Subjects with displacements, based on clinician assessment as defined in g) above, will be listed and the PMS results in the cycle after the displacement will be provided.

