| Tertiary: 4. Acceptability | 
 
a) Response on acceptability questionnaire/diary:         
 
Problems with insertion, including confirmation of placement
 
Aspects liked most and least by the female partner
 
Dislodgements reported by the female partner
 
Comfort reported by both partners during intercourse and whether discomfort, if reported, was bothersome and would keep the person from using the device again
 
 
 
 | Ovaprene® safety cycle & Ovaprene® PCT cycles                                 |
| 5. Fit                     | a) Proportion of subjects who can be fitted with Ovaprene®.   | Baseline PCT cycle  |
|                            | b) Proportion of subjects who can correctly insert, position, and remove the device using written instructions only.  | Baseline PCT
cycle, Ovaprene®
safety cycle &
Ovaprene® PCT
cycles |
|                            | c) Proportion of subjects who require assistance to correctly insert, position, and remove the device.  | Baseline PCT cycle, Ovaprene®   |

|   | safety cycle &
Ovaprene® PCT
cycles |
|---|---|
| 
 
d) Location of Ovaprene® in relation to the cervix as
determined by clinical exam; relationship of position to PCT
results, safety, and acceptability.
 
 | Ovaprene® safety cycle & Ovaprene® PCT    |
|   | cycles                                    |

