#### 3.1.3 Analysis Conventions

This section details general policies used for the statistical analyses. Departures from these general policies may be given in the specific detailed sections of this statistical analysis plan. When this situation occurs, the rules set forth in the specific section take precedence over the general policies. The following policies will be applied to all data presentations and analyses.

- Discrete variables' summary statistics will consist of the number and percent of responses in each category
- Continuous variables' summary statistics will include the sample size (number of non-missing observations), mean, median, standard deviation (SD), minimum and maximum, abbreviated as "6-number summary statistics", where minimum and maximum may be replaced with 25th and 75th percentiles, i.e., interquartile range (IQR), if desired.
- All mean values will be formatted to one more decimal place than the measured value. Standard deviation values will be formatted to two more decimal places than the measured value. Median values will be formatted to same decimal place as the measured values when that is possible without losing accuracy; otherwise, they will be formatted to one more decimal place than the measured values.
- All percentages will be rounded to one decimal place. The number and percent of responses
  will be presented in the form XX (XX.X), where the percentage is in the parentheses. The
  decimal of the percentage may be dropped due to space constraints when creating a table.
  The denominator for percentage calculations will be the number of non-missing observations,
  or the analysis population's sample size if no such number of non-missing observations is
  presented along with the categorical values.
- All by-subject data listings will be sorted for presentation in order of site number, subject number, and date of procedure or event.
- When necessary for analysis purposes, partial dates will be completed (i.e., turned into complete dates) using the most conservative approach: for example, if a concomitant medication start date had Month and Year parts only, it's assumed to be the first day of that month; while if the stop date had Month and Year parts only, it's assumed to be the last day of that month.
- All analysis and summary tables will have the population sample size in the column heading.
- Calculating change from Baseline to a visit will be done as follows:

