#### 4.2.1 Planned Tables

The format of each unique table is provided in a separate document of "Table Shells". Some outputs from statistical programming may be slightly different in layout from that illustrated in "Table Shells". The table shells will not be amended to match the actual tables in such cases.

| Table Number | Table Title   | Population |
|---------------------|---|-------------------|
| 14.1.1              | Summary of Subject Disposition and Reasons for Discontinuation  | All Screened      |
| 14.1.2              | Number and Percent of Subjects at Each Study Visit  | All Enrolled      |
| 14.1.2-E            | Number and Percent of Subjects at Each Visit and Time Point in East Virginia Medical School                 | All Enrolled      |
| 14.1.3-En           | Summary of Subject Disposition by Study Site for All Enrolled Population                                    | All Enrolled      |
| 14.1.3-Ca           | Summary of Subject Disposition by Study Site for Caya Population  | Caya              |
| 14.1.3              | Summary of Subject Disposition by Study Site  | Ovaprene          |
| 14.1.4-Ca           | Summary of Protocol Deviations by Cycle for Caya Population   | Caya              |
| 14.1.4              | Summary of Protocol Deviations by Cycle   | Ovaprene          |
| 14.1.5-En           | Summary of Demographics for All Enrolled Population   | All Enrolled      |
| 14.1.5-Ca           | Summary of Demographics for Caya Population   | Caya              |
| 14.1.5              | Summary of Demographics   | Ovaprene          |
| 14.1.6-En           | Summary of Medical History for All Enrolled Population  | All Enrolled      |
| 14.1.6-Ca           | Summary of Medical History for Caya Population  | Caya              |
| 14.1.6              | Summary of Medical History  | Ovaprene          |
| 14.1.7-En           | Summary of Gynecological History for All Enrolled Population  | All Enrolled      |
| 14.1.7-Ca           | Summary of Gynecological History for Caya Population  | Caya              |
| 14.1.7              | Summary of Gynecological History  | Ovaprene          |
| 14.1.8-En           | Summary of Contraceptive History for All Enrolled Population  | All Enrolled      |
| 14.1.8-Ca           | Summary of Contraceptive History for Caya Population  | Caya              |
| 14.1.8              | Summary of Contraceptive History  | Ovaprene          |

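### SAP 3.9 counts the wrong response level for positioning and removal, and Table 14.2.5 uses a population in which the BP3 fit rate is 100% by construction

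*SAP*

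**What the plan says.** SAP 2.4 lists three fit proportions that matter here. Endpoint 5a is the proportion who can be fitted, assessed in the baseline cycle. Endpoint 5b is "Proportion of subjects who can correctly insert, position, and remove the device using written instructions only". Endpoint 5c is "Proportion of subjects who require assistance to correctly insert, position, and remove the device".

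SAP 3.9 turns these into analyses using the Device Position CRF:
- Item a), fit: yes answers over all answers.
- Item b), insertion: the numerator is the written-only level.
- Item c), positioning: "Proportion of subjects who can correctly position the device using written and verbal instructions".
- Item d), removal: "Proportion of subjects who can correctly remove the device using written and verbal instruction and physical assistance".

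The response list has three levels in b) and c), but in d) it is printed with two: "Only written instructions, Written and verbal instructions and physical assistance".

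The general rule in SAP 3.1.3 is "Discrete variables' summary statistics will consist of the number and percent of responses in each category". The same section adds that, where a specific section departs from the general policies, "the rules set forth in the specific section take precedence over the general policies".

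Section 3.9 names no analysis population. The table index in SAP 4.2.1 assigns Table 14.2.5, the device fit summary, to the Ovaprene population. SAP 3.4 defines that as enrolled women who used Ovaprene, and All Enrolled leaves out screen failures.

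**The concern.** The three levels of one response scale appear to have been spread across the three handling steps, one level per step. The named figures for positioning and removal then do not measure unaided success, which is what 5b asks. Nor do they measure need for help: c) leaves out physical assistance and, on a three-level list, d) leaves out verbal help alone.

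For 5a, women the device does not fit are removed before the table population is formed, so the reported fit rate cannot fall whatever the true rate is.

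Protocol section 4 names both quantities as things the study will assess: how many women the device fits, and how many manage with written instructions only. They bear on the one-size design described there, and on the statement in protocol 11.1 that neither a sized fitting nor insertion by a professional is needed. A fit rate fixed at 100% and two mislabelled handling rates would misinform on those claims. No test, decision rule, primary endpoint or safety endpoint is affected.

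**Working it through.** The documents give no figure for these endpoints, so there is nothing to reproduce. The check compares definitions, then uses assumed counts to show size.

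**1. Numerators**

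| Step | Level needed for 5b | Level named in SAP 3.9 | Match |
|---|---|---|---|
| Insert, b) | written only | written only | yes |
| Position, c) | written only | written plus verbal | no |
| Remove, d) | written only | written, verbal and physical | no |

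For each step, proportion = women at the named level / women with an answer. Assume 25 answers per step (25 is the planned number of completers, used only for scale).

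- All 25 written-only: 5b level 25/25 = 100%; c) 0/25 = 0%; d) 0/25 = 0%.
- All 25 needing physical help: c) is again 0/25 = 0%, so c) cannot tell the best outcome from the worst.
- 20 written-only, 4 verbal, 1 physical: 5b level 20/25 = 80%; c) 4/25 = 16%. Item d) is 1/25 = 4% if the CRF offers three levels for removal, or (4 + 1)/25 = 20% if it offers only the two printed. In the same example the share needing any help, verbal or physical, is 5/25 = 20%.

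**2. Denominator for 5a**

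- The Ovaprene fit test is at BP3 (protocol 9.2.1 c and Appendix 3). A woman the device does not fit does not continue.
- Poor fit of either device is exclusion criterion 8 (protocol 8.2). No exclusion criterion may be met before enrolment, which comes at successful completion of the baseline cycle (protocol 8).
- A consented woman who does not meet eligibility criteria is a screen failure (protocol 7.5). All Enrolled omits screen failures, and the Ovaprene population is a subset of All Enrolled (SAP 3.4).
- Table 14.2.5 is built on that subset.

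Every woman in the table has therefore passed the test, and 5a = n/n = 100% unless a woman was enrolled in breach of eligibility (a deviation type listed in SAP 3.3).

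On the fit-tested denominator, 5a = fitted / (fitted + not fitted). Take 45 fitted, from the planned enrolment of about 45; the numbers not fitted are assumed.

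| Not fitted | 5a, all fit-tested | 5a, Ovaprene population |
|---|---|---|
| 2 | 45/47 = 95.7% | 100% |
| 4 | 45/49 = 91.8% | 100% |
| 8 | 45/53 = 84.9% | 100% |

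**3. Handling at BP3**

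Under protocol 9.2.1 c), women the device does not fit never attempt handling, so the relevant group for 5b and 5c at BP3 is women who fitted and attempted it. The response lists printed in SAP 3.9 show no level for a woman unable even with help. No figure can be given without the CRF.

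The documents also differ on where these endpoints belong. Protocol Table 4 places 5b and 5c at Visit 1, where only Caya is inserted. Protocol Table 5 lists only 5a among the fit endpoints for the baseline cycle. Protocol section 6 and SAP 2.4 list 5b and 5c there too, and protocol 14.2.6 refers to screened women. This is missing detail, and parts 1 and 2 do not depend on it.

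**The case against.** The strongest reply is that SAP 3.1.3 shows every category of a discrete variable by default, and its precedence clause applies only where a section departs from that default. Naming one level does not forbid showing the others. Section 3.9 also prints the response lists and uses one denominator rule, all who answered. The layout is held elsewhere: "The format of each unique table is provided in a separate document of" table shells, which are not available here. If the shell shows every level, written-only success and each degree of help could be read off step by step.

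This stands in part: the 0% result concerns the named figures, not necessarily everything the table will print. It does not correct the named figures. Items e) and f) of the same section ask for a full categorical summary, whereas b) to d) each define a single numerator, so the section distinguishes the two. Neither reading defines a result across the three steps together.

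On 5a, the denominator in item a) is everyone who answered the question, which taken alone would include women who failed the fit test. Once the table population is applied, those women are gone. The raw information does survive. SAP 3.2 summarises screen-failure reasons, and Listing 16.2.5.2 gives Device Position for All Screened. Criteria 8 and 9 cover either device, so the reason categories may not separate Ovaprene from Caya, but visit timing could: Caya is fitted at Visit 1 and Ovaprene at BP3. No planned table turns this into the 5a proportion.

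Two smaller points are fair. The two-level list in d) is probably a dropped level, because its stated numerator matches the third level printed in b) and c); the 20% branch is therefore the less likely one. Also, the synopsis and design sections describe recruiting up to approximately 45 women, so 45 passing BP3 is an assumption.

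**Conclusion.** The concern holds on both main points. The numerators in SAP 3.9 c) and d) contradict endpoint 5b and do not supply 5c; under complete unaided success they read 0% where 5b is 100%. The BP3 fit proportion in Table 14.2.5 is 100% by construction, barring an eligibility deviation, against 95.7% to 84.9% if 2 to 8 women fail the test alongside 45 who pass.

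All counts are assumed. The first conclusion rests on the text of 3.9 and could be softened by the table shells or the CRF. The second rests on applying the population in the table index as written. The consequence is limited to tertiary, descriptive endpoints, so this should be corrected but does not threaten the trial's main conclusions.

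**What to change.** - In SAP 3.9 b), c) and d), make the written-only level the 5b numerator at every step.
- For 5c, report the remaining levels for each step, separately and combined, and state whether verbal re-instruction counts as assistance.
- Check the removal response list against the CRF and print it in full.
- For 5a, use as denominator all women given the Ovaprene fit test at BP3, taken from the Device Position data.
- For 5b and 5c at BP3, use all women who fitted and attempted handling. Count those unable even with assistance as not successful where the CRF or the screen-failure reason identifies them; if neither does, say so under the table.
- State which device and visit the screened women in protocol 14.2.6 refers to.
- Keep the Ovaprene population for the OS and OP visits.

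The cost is SAP wording and one table population. The numerators and 5a need no new data, because Device Position is already listed for All Screened. Whether women unable to handle the device at BP3 can be counted depends on what was recorded.

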#### 14.2.6 Tertiary: Fit

The proportion of screened women who could correctly insert, position, and remove the device without assistance will be calculated for each visit at which it was assessed. The proportion who required assistance will also be calculated. The proportion of women in whom the device was found to be located over the cervix will be calculated for each visit at which it was assessed. The proportion of successful PCT visits at which the device was found to be located over the cervix will also be calculated. The proportion of visits in which adverse safety outcomes were recorded at which the device was found to be located over the cervix will be calculated. The proportion of participants who recorded adverse acceptability outcomes in whom the device was found not to be located over the cervix will be calculated.

Version: 06.00 (FINAL) Date: June 13, 2019

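### SAP 3.9 b) to d) fixes a different help level for each of insertion, positioning and removal, so as specified it gives neither fit endpoint 5b nor 5c

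*SAP*

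**What the plan says.** SAP 2.4 lists 5b as "Proportion of subjects who can correctly insert, position, and remove the device using written instructions only" and 5c as "Proportion of subjects who require assistance to correctly insert, position, and remove the device". Protocol 14.2.6 turns both into analysis commitments, by visit: "The proportion of screened women who could correctly insert, position, and remove the device without assistance will be calculated", and then "The proportion who required assistance will also be calculated".

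SAP 3.9 is where these should become derivations. Its items are:

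- b) "Proportion of subjects who can correctly insert the Ovaprene® device using written instructions only"
- c) "Proportion of subjects who can correctly position the device using written and verbal instructions"
- d) "Proportion of subjects who can correctly remove the device using written and verbal instruction and physical assistance"

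For each item the SAP names the CRF question and sets the numerator as the count of one response category. It counts clinicians who gave that answer over clinicians who answered, not women. No text combines the three answers within a woman, and none says what counts as requiring assistance. The one fit table planned is 14.2.5, on the Ovaprene population.

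**The concern.** Whether a woman can use the device from written instructions is a question the protocol raises in its Introduction, and 5b and 5c are the endpoints that answer it. If a programmer follows SAP 3.9 as written, the fit table will hold three proportions on three different scales, none of which is 5b or 5c.

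Item c) is also easy to misread. It is worded as the proportion able to position the device, but its numerator holds only the women who needed verbal help, so it falls as women do better.

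Defining 5b and 5c later from the listings would mean deciding, with the results in view, whether verbal re-instruction is assistance and who belongs in the denominator.

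**Working it through.** The plan states no figure on this point, so there is none to reproduce. The check compares definitions and then asks what the specified figures can determine.

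**Step 1. Which cells are specified (SAP 3.9).**

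| Step | Written only | Written and verbal | Physical help |
|---|---|---|---|
| Insert | b) | – | – |
| Position | – | c) | – |
| Remove | – | – | d) |

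Three of nine cells are named. 5b needs the first column for all three steps. 5c needs the third column for all three, and also the second if verbal help counts as assistance. Neither column is complete, so the mismatch remains even if 5b and 5c are read as three separate one-step proportions.

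**Step 2. What b), c) and d) determine.** Assumed rates, because the documents give none: 25 women (the approximate completer target), and at each step 20 written only, 3 verbal, 2 physical. SAP 3.9 would report b) 20/25 = 80%, c) 3/25 = 12%, d) 2/25 = 8%. Sharp bounds over all joint patterns of three steps by three levels that agree with those three figures:

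- all three steps written only: 0/25 to 20/25 (0% to 80%)
- any verbal or physical help: 5/25 to 25/25 (20% to 100%)
- any physical help: 2/25 to 25/25 (8% to 100%)

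The ranges are wide because c) leaves 25 − 3 = 22 women who could have positioned the device either unaided or with hands-on help. If all 25 women positioned it from the leaflet, c) would read 0/25.

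**Step 3. What full one-step tables would determine.** Suppose all nine cells were reported at the same assumed rates. For written-only proportions p1, p2, p3, the share passing all three steps lies between max(0, p1 + p2 + p3 − 2) and min(p1, p2, p3).

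- All three written only: 3 × 0.80 − 2 = 0.40, up to 0.80 (10/25 to 20/25). Independence would give 0.8³ = 0.512.
- Any help: 1 − 0.80 = 0.20 up to 1 − 0.40 = 0.60 (5/25 to 15/25).
- Any physical help: 2/25 if the same women need it each time, up to 3 × 2 = 6/25 (8% to 24%).
- At 90% per step: 3 × 0.90 − 2 = 0.70, up to 0.90.

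Full tabulation narrows the ranges but does not identify an all-steps result. That needs the three answers joined within each woman.

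**Step 4. Where the three answers can be joined.** Protocol 9.2.1 has the woman insert, position and remove the device at BP3, with re-instruction or help if needed, so all three answers arise at one visit. In the Ovaprene cycles she inserts at OS1 and OP1 (Protocol 9.4.1, 9.5.1). At OS5 and OP5 the text says only that the device is removed, not by whom.

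**Step 5. Denominator.** Protocol 14.2.6 refers to screened women. Table 14.2.5 uses the Ovaprene population, meaning enrolled women who used Ovaprene (SAP 3.4). A woman who cannot manage the device at BP3 even with help does not continue (Protocol 9.2.1, exclusion criterion 9), so that population leaves out the clearest failures.

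**The case against.** The best defence has four parts.

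**The endpoints may mean three separate skills.** Neither document states an all-steps composite, and the CRF asks three separate questions. That is fair: the all-steps reading is natural but not explicit. It does not rescue SAP 3.9, which gives no single help level for all three steps.

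**The table may show more than the text.** The section's list is introduced as what the analysis includes, the general convention in SAP 3.1.3 shows every category of a discrete variable, and items b), c) and d) name the first, second and third help level in turn, as if giving one example row each. The shell for Table 14.2.5 is in a separate document not available here. So a reader should not infer that 5b and 5c will certainly be missing from the output. But the same convention gives precedence to specific sections, and 3.9 names specific numerators. Even all the categories would not yield a joint result.

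**The data are not lost.** Listing 16.2.5.2 covers device position for all screened women, so 5b and 5c could be rebuilt. This stands, and it is why the repair is cheap. It leaves the definitions unsettled in advance.

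**The stakes are small.** Fit is tertiary and descriptive, with no test and no success criterion, in a study not sized on statistical grounds. This also stands.

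One further stronger claim fails: that removal is the only step with an assistance figure. If verbal re-instruction counts as assistance, c) is a partial one. Only for hands-on help is removal the sole step specified.

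**Conclusion.** The point holds as a specification error. The numerators stated in SAP 3.9 b) to d) do not give 5b or 5c on either reading of those endpoints. Written-only success is specified for insertion alone, written-only positioning is outside the numerator of c), and hands-on help with insertion or positioning is in no specified numerator.

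Its size cannot be estimated from the documents, which give no step-level rates. The 40% to 80% range rests on assumed rates of 80% per step and presumes fuller tables than SAP 3.9 specifies. Its lower end requires that no woman need help with more than one step. It shows that one-step figures do not determine the joint result and should not be read as an expected error. No primary or secondary conclusion depends on this. It should be corrected because two named endpoints and a protocol commitment lack a matching derivation.

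**What to change.** In SAP 3.9:

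1. Report all help levels for each of the three steps. Check the response options for removal against the CRF: item d) lists two where b) and c) list three, which may be a text slip.
2. At BP3, derive for each woman the highest help level needed over the three steps. 5b is written instructions only at every step. 5c is any step above that, shown separately as verbal re-instruction only and physical assistance, with the SAP stating which counts as assistance. Protocol 9.2.1 names re-instruction and assistance as two things, so this has to be settled. If verbal help counts, 5c is the complement of 5b among women who complete all three steps.
3. Use as denominator all women who attempted the device at BP3, in line with Protocol 14.2.6, rather than the Ovaprene population. Women unable to complete a step even with help do not meet 5b and get their own row. The response options quoted in SAP 3.9 have no such category, so this row may have to come from the eligibility record.
4. Count women, not clinicians.
5. At later visits, report only the steps the woman herself performed, and label them.

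The cost is one derived variable and a few table rows, with no new data collection foreseen. The downside for the sponsor is that 5b may come out less favourable than the insertion figure alone.
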